6.1.5.6 TSQM-9 questionnaire

The TSQM-9 is a self-administered PRO with Likert type response options that assesses satisfaction with medication use over 3 domains: Effectiveness (items 1 through 3), Convenience (items 4 through 6), and Global Satisfaction (items 7 through 9). Each domain score ranges from 0 to 100, with higher scores indicating increased satisfaction. The instrument is not disease specific. The TSQM 9 and previous versions have undergone qualitative and psychometric testing and were found to be valid and reliable.

- The Global Satisfaction subscore is based on Item 7, Item 8 and Item 9 and is calculated as follow:

$$[(\text{Item 7} + \text{Item 8} + \text{Item 9} - 3)/14]*100$$

If either Item 7 or Item 8 is missing: [(sum of the 2 completed items – 2)/10]*100

If Item 9 is missing: [(Item 7 + Item 8 – 2)/8]*100

- The Effectiveness subscore is based on Item 1, Item 2 and Item 3 and is calculated as follow:
[(Item 1 + Item 2 + Item 3 – 3)/18]*100

If one Item is missing: [(sum of the 2 completed items – 2)/12]*100

- The Convenience subscore is based on Item 4, Item 5 and Item 6 and is calculated as follow:
[(Item 4 + Item 5 + Item 6 – 3)/18]*100

If one Item is missing: [(sum of the 2 completed items – 2)/12]*100

6.1.6 AEs of Interest

Table 6–5: AEs of Interest selection criteria

No	Event (also included in Title of TFL output)	Selection criteria
1	Hypersensitivity reactions	SMQ='Hypersensitivity' (narrow scope)
2	Anaphylactic reactions	SMQ= 'Anaphylactic reaction' and TEAEs meeting at least one of the following criteria where the different terms (within each sub-category) occur on the same date or on 2 consecutive days, under the condition that the zilucoplan treatment is still ongoing at the first of these 2 days. 1. If a participant reports any TEAE which codes to a PT included in Category A, then the event will be flagged as an anaphylactic reaction. 2. If a participant reports any TEAE which codes to a PT included in Category B AND reports any TEAE which codes to a PT included in Category C, and both TEAEs have the same start date or on 2 consecutive days , then both events will be flagged as anaphylactic reactions. If a participant reports any TEAE which codes to a PT included in Category D AND reports (either a TEAE which codes to a PT included in Category B OR a TEAE which codes to a PT included in Category C), and both TEAEs have the same start date or on 2 consecutive days , then both events will be flagged as anaphylactic reactions.
3	Drug related hepatic disorders	TEAEs in: SMQ narrow scope='Drug related hepatic disorders - comprehensive search' but excluding these 2 sub- SMQs: "Liver neoplasms, benign (incl cysts and polyps) (SMQ)" and "Liver neoplasms, malignant and unspecified (SMQ)".

4	Malignancies or unspecified tumours	TEAEs in: SMQ= “Malignant or unspecified tumours (SMQ)” or “Malignant tumours (SMQ)” Note: the events included in the “Malignant tumours” table will be a subset of the events included in the “Malignant or unspecified tumours” table. While the “Malignant tumours (SMQ)” is most relevant, “Malignant or unspecified tumours (SMQ)” must be reviewed for potential malignancies. Table
5	Injection site reactions	TEAE with HLT = 'Injection site reactions' or HLT = Administration site reactions NEC'

Table 6-6: Anaphylactic Reactions Categories

Category	Preferred Term
A	ANAPHYLACTIC REACTION
	ANAPHYLACTIC SHOCK
	ANAPHYLACTIC TRANSFUSION REACTION
	ANAPHYLACTOID REACTION
	ANAPHYLACTOID SHOCK
	CIRCULATORY COLLAPSE
	DIALYSIS MEMBRANE REACTION
	KOUNIS SYNDROME
	PROCEDURALSHOCK
	SHOCK
	SHOCK SYMPTOM
	TYPE 1 HYPERSENSITIVITY
B	ACUTE RESPIRATORY FAILURE
	ASTHMA
	BRONCHIAL OEDEMA
	BRONCHOSPASM
	CARDIO-RESPIRATORY DISTRESS
	CHEST DISCOMFORT
	CHOKING
	CHOKING SENSATION
	CIRCUMORAL OEDEMA
	COUGH
	COUGH VARIANT ASTHMA
	CYANOSIS
	DYSPNOEA
	ENHANCED RESPIRATORY DISEASE
	HYPERVENTILATION

Table 6–6: Anaphylactic Reactions Categories

Category	Preferred Term
	IRREGULAR BREATHING
	LARYNGEAL DYSPNOEA
	LARYNGEAL OEDEMA
	LARYNGOSPASM
	LARYNGOTRACHEAL OEDEMA
	MOUTH SWELLING
	NASAL OBSTRUCTION
	OEDEMA MOUTH
	OROPHARYNGEAL OEDEMA
	OROPHARYNGEAL SPASM
	OROPHARYNGEAL SWELLING
	PHARYNGEAL SPASM
	PHARYNGEAL SWELLING
	RESPIRATORY ARREST
	RESPIRATORY DISTRESS
	RESPIRATORY FAILURE
	REVERSIBLE AIRWAYS OBSTRUCTION
	SENSATION OF FOREIGN BODY
	SNEEZING
	STRIDOR
	SWOLLEN TONGUE
	TACHYPNOEA
	THROAT TIGHTNESS
	TONGUE OEDEMA
	TRACHEAL OBSTRUCTION
	TRACHEAL OEDEMA
	UPPER AIRWAY OBSTRUCTION
	WHEEZING
C	ALLERGIC OEDEMA
	ANGIOEDEMA
	CIRCUMORAL SWELLING
	ERYTHEMA
	EYE OEDEMA
	EYE PRURITUS
	EYE SWELLING
	EYELID OEDEMA
	FACE OEDEMA
	FLUSHING

Table 6–6: Anaphylactic Reactions Categories

Category	Preferred Term
	INJECTION SITE URTICARIA
	LIP OEDEMA
	LIP SWELLING
	NODULAR RASH
	OCULAR HYPERAEMIA
	OEDEMA
	OEDEMA BLISTER
	PERIORBITAL OEDEMA
	PERIORBITAL SWELLING
	PRURITUS
	PRURITUS ALLERGIC
	RASH
	RASH ERYTHEMATOUS
	RASH PRURITIC
	SKIN SWELLING
	SWELLING
	SWELLING FACE
	SWELLING OF EYELID
	URTICARIA
	URTICARIA PAPULAR
D	BLOOD PRESSURE DECREASED
	BLOOD PRESSURE DIASTOLIC DECREASED
	BLOOD PRESSURE SYSTOLIC DECREASED
	CARDIAC ARREST
	CARDIO-RESPIRATORY ARREST
	CARDIOVASCULAR INSUFFICIENCY
	DIASTOLIC HYPOTENSION
	HYPOTENSION
	HYPOTENSIVE CRISIS
	POST PROCEDURAL HYPOTENSION

6.1.7 Potentially Clinically Significant Criteria for Safety Endpoints

No additional information.

6.1.8 Extent of Exposure

The time to study withdrawal is defined as Date of study withdrawal – date of first IMP + 1.

The compliance between 2 clinic visits will be calculated as: (number of syringes dispensed at the previous clinic visit – number of unused syringes returned in clinic – total number of malfunctioned syringes)/(Date the syringes are returned in clinic – Date the syringes are dispensed in clinic)*100.

The overall compliance in the Main Treatment Period will be calculated as: (total number of syringes dispensed – total number of unused syringes – total number of malfunctioned syringes) / (Date the last syringes are returned in clinic in the Main Treatment Period – Date the first syringes are dispensed in clinic)*100.

For participants entering in the Extension Treatment Period, the overall compliance in the Overall Treatment Period will be calculated as: (total number of syringes dispensed – total number of unused syringes – total number of malfunctioned syringes+1)/(Date of last drug administration – Date the first syringes are dispensed in clinic in the Main Treatment Period+1)*100.

If the participant was (early) withdrawn, then the date to be considered in the calculation of compliance as the end of exposure period will be the date of last administration of Zilucoplan and not the date the participant returned the syringes in clinic. Then, the compliance will be calculated as follows: (number of syringes dispensed at the previous clinic visit – number of unused syringes returned in clinic – total number of malfunctioned syringes+1)/(Date of last drug administration – Date the syringes are dispensed in clinic + 1)*100.

Of note, the number of syringes dispensed at each visit will be derived based on the number of kits dispensed at that visit, assuming that each kit contains 7 single dose syringes to be used for the daily dosing.

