**Table 6–1: Treatment administered**

Arm name	Zilucoplan
Intervention name	Zilucoplan
Type	Drug
Dose formulation	Pre-filled syringe
Unit dose strength(s)	16.6mg in 0.416mL 23.0mg in 0.574mL 32.4mg in 0.810mL
Dosage level	0.3mg/kg/day
Route of administration	Subcutaneous injection
Use	Experimental
IMP	IMP
Sourcing	Provided centrally by the Sponsor
Packaging and labeling	Study medication will be provided in kits containing 7 prefilled syringes. Each syringe and kit will be labeled as required per country requirement.
Excipients	
Former names	RA101495

IMP=investigational medicinal product; NIMP=noninvestigational medicinal product

Zilucoplan 0.3mg/kg/day administered SC is the selected dose for this study. As in other ZLP studies, the dose presentation will be selected using the following weight brackets ([Table 6–2](#)).

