### **6.2.1 Drug accountability**

The eCRF will be used to record study medication dispensing and return information on a by-participant basis and will serve as source documentation during the course of the study. Details of any study medication lost, damaged (due to breakage or wastage), not used, partially used, disposed of at the study site, or returned to the Sponsor or designee must also be recorded on the appropriate forms. All supplies and pharmacy documentation must be made available throughout the study for UCB (or designee) to review.

The Investigator (or designee) is responsible for retaining all used, unused, and partially used containers of study medication until returned or destroyed.

The Investigator may assign some of the Investigator's duties for drug accountability at the study site to an appropriate pharmacist/designee.

The Investigator must ensure that the study medication is used only in accordance with the protocol.

Periodically, and/or after completion of the clinical phase of the study, all used (including empty containers/partially used), unused, damaged, and/or expired study medication must be reconciled and either destroyed at the site according to local laws, regulations, and UCB standard operating procedures (SOPs) or returned to UCB (or designee). Study medication intended for the study cannot be used for any other purpose than that described in this protocol.

For further details about drug accountability, refer to the IMP Handling Manual.

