6.1.8 Extent of Exposure	
 The denomination for the calculation of the reference period with respect to treatment compliance is changed as follows: Compliance between 2 study visits: Day of the visit in clinic – Day of the previous visit in clinic +1) changed to: Date the syringes are returned in clinic – Date the syringes are dispensed in clinic. 
Overall Compliance in the Main Treatment Period: Day of the last visit in clinic in the Main Treatment Period – Day of the baseline visit + 1 changed to: Date the last syringes are returned in clinic in the Main Treatment Period – Date the first syringes are dispensed in clinic
 
Compliance in the Overall Treatment Period: Day of the last visit in clinic in the Extension Treatment Period – Day of the baseline visit + 1 changed to: Date the last syringes are returned in clinic in the Extension Treatment Period – Date the first syringes are dispensed in clinic in the Main Treatment Period
 
 The following text is added: Of note, the number of syringes dispensed at each visit will be derived based on the number of kits dispensed at 	
 To adjust the compliance definition so that injections administered in a clinic visit will be part of the compliance measures with respect of the next time interval. Example: injections performed on Week 2 will be considered for the compliance between week 2 and week 12.

	
that visit, assuming that each kit contains 7 single dose syringes to be used for the daily dosing.
	
 • To further clarify the derivation of treatment compliance.
6.2.3 Marked Abnormalities Electrocardiogram (ECG)	
 • The top label row of Table 6-10: has been updated to Treatment Emergent Markedly Abnormal Criteria. • The underlined text is added the footnote of Table 6-10: Marked Abnormalities (ECG) Note: Treatment-emergent Markedly Abnormal is defined as meeting the criteria at any post-Baseline visit after the first dose of IMP and not meeting the criteria at Baseline. 	
 • To capture the table contents. • To update and correct the Treatment Emergent Markedly Abnormal (TEMA) definition.

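### SAP 6.1.8: under the SAP's own counting convention, the numerator +1 in the withdrawn and Overall Treatment Period compliance formulas credits one dose too many

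*SAP*

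**What the plan says.** SAP 6.1.8 (Extent of Exposure) starts every numerator from syringes dispensed, less unused, less malfunctioned. The formulas then differ in two ways: the date at which the interval ends, and whether 1 is added.

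- Between two clinic visits: "total number of malfunctioned syringes)/(Date the syringes are returned in clinic – Date the syringes are dispensed in clinic)*100".
- Main Treatment Period: the same numerator over "Date the last syringes are returned in clinic in the Main Treatment Period – Date the first syringes are dispensed in clinic)*100".
- Overall Treatment Period, for participants who enter the Extension: "total number of malfunctioned syringes+1)/(Date of last drug administration – Date the first syringes are dispensed in clinic in the Main Treatment Period+1)*100".
- (Early) withdrawn participants: "total number of malfunctioned syringes+1)/(Date of last drug administration – Date the syringes are dispensed in clinic + 1)*100".

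The number dispensed is derived from kits, "assuming that each kit contains 7 single dose syringes to be used for the daily dosing". Protocol Table 6–1 describes the supply in the same way: "Study medication will be provided in kits containing 7 prefilled syringes".

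The SAP version history gives reasons for the two most recent changes to this section. Amendment 3.0, which introduced the between-visit and Main formulas now in force, illustrates its rule by saying that "injections performed on Week 2 will be considered for the compliance between week 2 and week 12". Amendment 4.0 introduced the last-dose formulas. Its reason is that syringes may be returned after the last dose, so the interval should stop at the last dose. It gives no reason for adding 1 to the numerator.

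**The concern.** An interval that ends on a dosing day needs an inclusive day count, so the +1 in the denominator is expected. The numerator is not a difference of dates. It is a count of syringes used, and such a count needs no inclusive correction. If the dose on the dispensing day came from the kits handed out that day, it is already in that count.

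Two things are then at stake. Full adherence would be reported above 100%, and SAP 6.1.8 states no cap (the truncation at 100% in SAP 5.1 is for confidence limits). The withdrawn and Overall figures would also not be comparable with the between-visit and Main figures. The discrepancy is largest for short exposures, that is, for early withdrawals in a planned sample of 20.

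**Working it through.** The documents state no compliance value, so there is no figure to reproduce. The check evaluates the formulas at known adherence.

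**Inputs.** Dispensing and visit days are 1, 15 and 84 (protocol Table 1–2: Baseline, Week 2, Week 12). Dosing is one syringe per day. A visit-day dose belongs to the interval that starts at that visit (SAP version history, Amendment 3.0). Assumption: the dispensing-day dose comes from the kits dispensed that day. No syringes malfunction.

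**Step 1: formulas without +1, full adherence.**
- Baseline to Week 2: doses on Days 1–14 = 14; 15 − 1 = 14; 14/14 = 100%.
- Week 2 to Week 12: doses on Days 15–83 = 69; 84 − 15 = 69; 69/69 = 100%.
- Main Treatment Period: doses on Days 1–83 = 83; 84 − 1 = 83; 83/83 = 100%.

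So the convention and these two formulas agree.

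**Step 2: formulas with +1.** Let N = last dose date − dispensing date + 1, and let k be the number of missed doses. Syringes used = N − k. The SAP formula gives (N − k + 1)/N. The true value is (N − k)/N. The difference is 1/N, or 100/N percentage points, whatever k is.

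| N (days) | SAP, k=0 | True, k=0 | SAP, k=1 | True, k=1 |
|---|---|---|---|---|
| 5 | 6/5 = 120.0% | 100% | 100% | 4/5 = 80.0% |
| 14 | 15/14 = 107.1% | 100% | 100% | 13/14 = 92.9% |
| 69 | 70/69 = 101.4% | 100% | 100% | 68/69 = 98.6% |
| 168 | 169/168 = 100.6% | 100% | 100% | 167/168 = 99.4% |

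Two missed doses appear as one: for N=14, 13/14 = 92.9% is shown and 12/14 = 85.7% is true.

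**Step 3: numerator +1 removed.** (N − k)/N gives 100% at full adherence for every N, and the true value otherwise.

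**Step 4: does another source for the visit-day syringe rescue the formulas?**
- Every visit-day dose from separate clinic stock: Baseline to Week 2 gives 13/14 = 92.9% at full adherence, so the between-visit formula fails.
- Only the Day 1 dose separate, later visit-day doses from the new kits: the Overall formula gives 100%, but the Main formula gives 82/83 = 98.8%, and a withdrawal after Week 2 still gives (N + 1)/N.

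**Step 5: Week 12.** Footnote x of Table 1–2 limits Week 12 dispensing to participants who continue into the Extension. If a participant who does not continue is dosed at Week 12 from the existing kit, the Main formula gives 84/83 = 101.2%.

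**The case against.** The strongest reply is that one counting rule does reconcile all four formulas. Suppose the Day 1 dose is outside the dispensed kits and each later visit-day dose comes from the outgoing kit. Full adherence then gives Days 2–15 = 14 over 14, Days 16–84 = 69 over 69, and Days 2–84 = 83 over 83. For a last dose on Day L, a withdrawal after Week 2 gives (L − 15 + 1)/(L − 15 + 1), and the Overall formula gives (L − 1 + 1)/(L − 1 + 1). A reader might infer that no single rule can make the formulas agree, and that inference is wrong. Under this rule, deleting the +1 would report a fully adherent five-dose withdrawal as 4/5 = 80%. SAP 5.4.1 gives this reading some support: it takes missed doses from the drug administration page after Day 1.

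The rule is still hard to accept. It contradicts the Week 2 example in the Amendment 3.0 rationale. It needs a Day 1 supply that neither document describes. For a withdrawal after Week 2 it also counts the Day 15 dose twice, once in the interval that ended at Week 2 and again as the +1. What stands is that no passage says outright which kit supplies a visit-day dose. The Amendment 3.0 example says which interval the injection counts toward, and it predates the last-dose formulas. The correction should therefore be conditional.

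A reader might also infer that a missed dose disappears from the report. It does not: SAP 5.4.1 separately summarizes missed doses as expected minus received, with no +1, and lists all drug administration details. The same participant could thus show one missed dose and 100% compliance.

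Finally, protocol 6.2.1 requires a record of "Details of any study medication lost, damaged (due to breakage or wastage), not used, partially used" and further categories, and a reader might conclude that the formulas wrongly credit such syringes as doses. The documents do not settle that. They do not say how far the malfunctioned category overlaps with these, and subtracting a partially used syringe would score a partial dose as none.

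**Conclusion.** The point holds under the SAP's stated convention, together with the assumption that the dispensing-day dose comes from the kits dispensed that day. That assumption is not stated, but it fits the kit-only supply. Each result from the withdrawn and Overall formulas is then too high by exactly one dose: 20 points at 5 days, 7.1 at 14, 1.4 at 69 and 0.6 at 168. It matters mainly for early withdrawals and is negligible over long extension exposure.

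The consequence is limited to a descriptive output in the appendix of non-key specifications. The TEAE endpoints, the study-withdrawal endpoint, the MG-ADL noninferiority test, the analysis sets and the missed-dose summary do not use the compliance percentage. The major-deviation threshold in protocol 6.4 is ten consecutive missed doses, not a percentage. The formula should be corrected because it gives wrong values and the correction is nearly free. It does not put the trial's conclusions in doubt.

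**What to change.** First confirm that the dispensing-day dose is taken from the kits dispensed that day, and say so in SAP 6.1.8. If it is, delete the numerator +1 from the withdrawn and Overall formulas and keep the denominator +1:

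(dispensed − unused − malfunctioned) / (last administration date − dispensing date + 1) × 100,

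with the first dispensing date used for the Overall Treatment Period.

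If it is not, state which dose the +1 represents and align all four formulas so that full adherence equals 100%. In either case, specify how the Week 12 dose is counted in the Main formula for participants who do not enter the Extension.

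The cost is a short wording change to the SAP and a small programming edit. No new data are needed. Some reported compliance values will fall slightly.

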6.1.9 COVID-19 terms

Table 6.7: Preferred Terms to define COVID-19 infection

Name	Scope
Asymptomatic COVID-19	Narrow
COVID-19	Narrow
COVID-19 pneumonia	Narrow
COVID-19 treatment	Narrow
Post-acute COVID-19 syndrome	Narrow
SARS-CoV-2 antibody test positive	Narrow
SARS-CoV-2 RNA increased	Narrow
SARS-CoV-2 sepsis	Narrow
SARS-CoV-2 test false negative	Narrow
SARS-CoV-2 test positive	Narrow
SARS-CoV-2 viraemia	Narrow
Suspected COVID-19	Narrow

6.2 Appendix 2: Abnormality criteria for Laboratory, Vital Sign and Electrocardiogram Parameters

6.2.1 Laboratory Assessments Marked Abnormality Criteria

The following criteria will be applied in the determination of marked abnormalities for laboratory parameters. They are based on Version 5 of the Common Terminology Criteria for Adverse Events (CTCAE) grade 3 or higher criteria unless otherwise noted. If both high and low criteria are shown for a parameter, the criteria should be summarized separately in tabular or graphical summaries.

Table 6–8: Laboratory Marked Abnormalities

Parameter	Unit (conventional)	Unit (Standard)	Marked Abnormality Criteria
Hematology			
Hemoglobin	g/dL	g/L	<8.0 g/dL; <80 g/L
WBC (Leukocytes)	10 ⁹ /L	10 ⁹ /L	Low: <2.0 x 10 ⁹ /L High: >100 x 10 ⁹ /L
Lymphocytes Absolute	10 ⁹ /L	10 ⁹ /L	Low: <0.5 x 10 ⁹ /L High: >20 x 10 ⁹ /L
Neutrophils Absolute	10 ⁹ /L	10 ⁹ /L	<1.0 x 10 ⁹ /L
Platelets	10 ⁹ /L	10 ⁹ /L	<50.0 x 10 ⁹ /L
Eosinophils	10 ⁹ /L	10 ⁹ /L	≥1.5 x 10 ⁹ /L
Biochemistry			
AST	U/L	U/L	>5.0 x ULN if Baseline value is normal; >5.0 x Baseline value if Baseline is abnormal
ALT	U/L	U/L	>5.0 x ULN if Baseline value is normal; >5.0 x Baseline value if Baseline is abnormal
ALP	U/L	U/L	>5.0 x ULN if Baseline value is normal; >5.0 x Baseline value if Baseline is abnormal
Bilirubin (total)	mg/dL	umol/L	>3.0 x ULN if Baseline value is normal > 3.0 x Baseline value if Baseline is abnormal
Creatinine	mg/dL	umol/L	>3.0 x ULN
Estimate glomerular filtrate rate (eGFR) ^a	mL/min/1.73 m ²	mL/min/1.73 m ²	<29 mL/min/1.73m ²

Parameter	Unit (conventional)	Unit (Standard)	Marked Abnormality Criteria
Glucose ^b	mg/dL	mmol/L	Low: <40 mg/dL; < 2.2 mmol/L High: >250 mg/dL; >13.9 mmol/L
Potassium	mEq/L	mmol/L	Low: <3.0 mmol/L High: >6.0 mmol/L
Sodium	mEq/L	mmol/L	Low: <125 mmol/L High: >155 mmol/L
Amylase	U/L	U/L	>2.0 x ULN
Lipase	U/L	U/L	>2.0 x ULN

ALT= alanine aminotransferase; AST = aspartate aminotransferase; CRP = C-reactive protein; dL = deciliter; L = liter; mg = milligram; mmol = millimoles; μ g = microgram; U = unit; ULN = upper limit of normal

Note: Marked abnormality criteria are defined by Grade 3 or higher events according to the Common Terminology for Adverse Events (CTCAE), Version 5.0, November 17, 2017 unless otherwise noted.

^a eGFR is calculated using the Chronic Kidney Disease Epidemiology Collaboration or CKD-EPI formula (https://qxmd.com/calculate/calculator_251/egfr-using-ckd-epi) which is $eGFR = 141 * \min(Scr/\kappa, 1)^\alpha * \max(Scr/\kappa, 1)^{-1.209} * 0.993^{\text{Age}} * 1.018$ [if female] * 1.159 [if black]; where Scr is serum creatinine (mg/dL), κ is 0.7 for females and 0.9 for males, α is -0.329 for females and -0.411 for males, min indicates the minimum of Scr/ κ or 1, and max indicates the maximum of Scr/ κ or 1. For derivation from values in standard units (umol/L) the κ values are 61.9 for females and 79.6 for males. Subjects with missing race should be considered as non-black for eGFR calculation.

^b Glucose high criterion defined by Grade 3 and higher events according to CTCAE, Version 4.03, June 14, 2010

